### **Secondary outcome analysis**

In this part of the analysis, the aim is to answer the research question: did the Restorative Mentoring intervention (treatment) reduce difficulties and self-reported behaviour measures according to the SDQ and SRDS questionnaires, when compared to the Restorative Choices intervention (control). Furthermore, do these reductions differ by sex, ethnicity, and referral source.

The secondary outcomes for this analysis will include the CYP's emotional and behavioural difficulties and self-reported delinquency.

Emotional and behavioural difficulties are measured by the following three variables:

- 1) Internalizing score – measured on a scale from 0-20
- 2) Externalizing score – measured on a scale from 0-20
- 3) Total difficulties score – measured on a scale from 0-40

Self-reported delinquency is measured by:

4) Variety of delinquency - measured as the sum of the overall categories of delinquency  
Range: 0-19.

5) Volume of delinquency - measured as the sum of magnitudes of delinquency, over all  
categories Range: 0-198.

These variables will be compared across the treatment and control groups to test the null hypothesis of equal means against the two-sided alternative.

The regression analysis takes the form

$$Y_i = \alpha + \beta T_i + Z_i' \gamma + u_i \quad (2)$$

where  $Y_i$  is the secondary outcome for individual  $i$  (one of the aforementioned SDQ and SRDS variables).  $T_i$  is an indicator variable equal to 1 if  $i$  was assigned to treatment and 0 if  $i$  was assigned to the control group.  $Z_i$  is a vector of individual characteristics that are not affected by the intervention (sex, age, ethnicity, district, prior contact with the police, and referral source).  $u_i$  represents the random errors, which are not observed. Given that  $Y_i$  is a continuous variable we will employ a linear regression. The key assumptions that we will use is that the observations are independent to each other, there is mean independence  $E(u_i|T_i, Z_i) = 0$ , and that not all CYP have identical  $T_i$  and  $Z_i$  (no perfect multicollinearity). These assumptions are weak and easily satisfied.

This part of the analysis will be exploratory as we will only have outcome measures for CYP who complete the survey at the end of the treatment. Therefore, we will obtain an estimate of the treatment's effect for those who finish the treatment. Additionally, it is important to acknowledge potential limitations in terms of statistical power since the sample size in this case will be smaller.

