Baseline for secondary outcome	variable	
The secondary outcomes will be the CYP's emotional and behavioural difficulties and self-reported delinquency.
 
Emotional and behavioural difficulties are measured by the following three variables:
 
 
1) Internalizing score
 
2) Externalizing score
 
3) Total difficulties
 
 
Self-reported delinquency is measured by:
 
 
4) Variety of delinquency
 
5) Volume of delinquency
 

	measure (instrument, scale, source)	
The first three scores are measured with the Strengths and Difficulties Questionnaire (SDQ) and the last two (4 & 5) are measured with the Self-Reported Delinquency Scale (SRDS) questionnaire.
 
The SDQ and SRDS are completed by CYP at the start of the intervention.
 
Scales are 0-20 for the internalizing and externalizing scores and 0-40 for the total difficulties score.
 
Variety of delinquency ranges from 0-19 and volume of delinquency ranges from 0-198 (this excludes the scoring for Question 16, which is different from the other questions).

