### Sample size calculations overview

	Protocol	Randomisation
Minimum Detectable Effect Size (MDES)	0.3	0.3
Alpha	0.05	0.05
Power	0.8	0.8

		Protocol	Randomisation
One-sided or two-sided?		Two-sided	Two-sided
Number of participants	intervention	176	176
	control	176	176
	total	352	352

The planned number of the trial participants is 352 CYP in its one year of implementation, 176 in the RM group and 176 in the RC group. The sample size is such that the trial is sufficiently powered to detect a Cohen’s d of at least 0.3 with probability 80%, which is in line with the funder guidelines and the previous literature.

The “simple” randomisation method will be used, which is a robust method against selection and accidental biases. We will use the statistical software package Matlab to implement the randomisation. Automated randomisation will ensure that the process is transparent and reproducible.

The above rest on the assumption that the alpha is equal to 0.05 and that the power is equal to 0.8. The minimum detectable effect size is equal to 0.3 as measured by Cohen’s d.

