### Primary outcome analysis

The aim of the analysis is to answer the research question: did the Restorative Mentoring intervention (treatment) reduce post-treatment contact with the police compared to the Restorative Choices intervention (control)?

The primary outcome for this study is contact with the police, defined as the number of times the CYP appear in the police data as perpetrators, victims or for missing person episodes. These data will be taken from Greater Manchester Police administrative records.

Contact with the police is a discrete count variable starting at 0. These data will be collected one month before the trial ends, for a period 1 year prior to the recruitment date and for 3 months after completion of the intervention for all CYP.

It should be noted that the primary outcome, which is police contact with the CYP, is susceptible to biases in reporting and recording of crimes. These biases may stem from a number of factors, including characteristics of both the victim and the offender, such as ethnicity and gender. Nevertheless, we anticipate that the RCT design remains robust to these biases, as randomisation into the treatment and control groups is conducted independently of the police's reporting and recording of crimes.

There are two ways of analysing the data, depending on the distribution assumed for the dependent variable, which is total police contacts. As a discrete count random variable, it may be assumed to follow a Poisson or Negative Binomial distribution. However, if the mean of that distribution is far from 0, the Poisson and Negative Binomial distributions may be approximated by the continuous normal distribution. It is not clear a priori which distribution will be the better approximation, and therefore we consider below both scenarios. In any case, we do not expect major differences; the issue of whether a variable should be treated as continuous or discrete has received much attention in the randomized control trial literature and the main finding is that unless the outcome is binary or it is a "time to a first event", information will not be lost when treating a count variable as a continuous one, see, e.g. Herbison et al. (2015).

For the analysis, the headline estimate will be derived from an intention to treat effect (ITT), denoted by  $\beta$  in the regression:

$$g[E(Y_i|T_i)] = \alpha + \beta T_i,$$

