where  $Y_i$  is the primary outcome for individual  $i$ , and  $T_i$  is an indicator variable equal to 1 if person  $i$  was assigned to treatment and 0 if person  $i$  was assigned to the control group. The function  $g$  is the link function and is equal to the natural logarithm function if the dependent variable is assumed to be Poisson or Negative Binomial.

Hypothesis testing in the above regression complies with the power predictions of the study. The effect size will be measured by the Incidence Rate Ratio if the data are assumed to be Poisson or Negative Binomial, and by Cohen's  $d$  if they are assumed approximately normal. If the data are Poisson/Negative Binomially distributed, the necessary sample size to detect a "small" effect of at least 1.22, see e.g. Cohen (1992) and Olivier et al. (2017), with  $\alpha=0.05$  and

80% power is 322 CYP equally split between the treatment and control groups. Alternatively, if the data are assumed to be normally distributed, then to detect a “small” effect size of at least 0.3 is 352 CYP. Therefore, a sample of 352 CYP will lead to as sufficiently powered study irrespective of the data distributional assumption.

We will additionally estimate a regression with covariates:

$$g[E(Y_i|T_i, Z_i)] = \alpha + \beta T_i + Z_i' \gamma,$$

where  $Z_i$  is a vector of individual characteristics that are not affected by the intervention (sex, age, ethnicity, district, the number of contacts with the police in the year prior to referral, and referral source). The analysis below depends on the over-arching assumption that the sample of observations are independent to each other. This is reasonable as the sample is only a small subset of the whole population.

The dependent variable here is a count variable and it is highly likely that the lower values will have much higher frequency, in other words it is heavily skewed to the right. This feature of the data suggests that they are best analysed using Poisson regression. Mathematically, the Poisson regression takes the form:

$$Y_i | \lambda_i \sim Poi(\lambda_i)$$

where  $\lambda_i = \alpha + \beta T_i + Z_i' \gamma$ .

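### Baseline SDQ and SRDS scores enter none of the planned models, and the baseline police-contact count is left out of the headline primary model although an additional model already includes it

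*SAP*

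**What the plan says.** **Secondary outcomes.** The SAP's Design overview defines the baseline for these outcomes: "The SDQ and SRDS are completed by CYP at the start of the intervention". Table 1 of the Protocol puts this data collection (Step 4) ahead of randomisation (Step 5), and the Protocol's Compliance section requires the same order. Equation (2) in the SAP's Secondary outcome analysis contains treatment and a covariate vector made up of "sex, age, ethnicity, district, prior contact with the police, and referral source". No baseline SDQ or SRDS score is listed. The Longitudinal follow-up analyses section applies the same analysis at six months. The Imbalance at baseline section tests the same kinds of characteristics and also leaves the scores out.

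**Primary outcome.** The SAP states that "the headline estimate will be derived from an intention to treat effect (ITT"), and the equation that follows has the treatment indicator as its only regressor. It then says: "We will additionally estimate a regression with covariates". That second model includes the number of police contacts in the year before referral. The Analysis section of the Protocol writes the ITT effect in an equation with covariates, past offences among the examples, and also plans simple differences in means. Randomisation is simple and unstratified in both documents.

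**The concern.** The baseline value of a repeated score or count is usually among its strongest predictors. Leaving it out keeps explainable variation in the residual, so the standard error is larger than it need be. It also leaves any chance imbalance on that variable in the estimate, and simple randomisation without strata does nothing to limit such imbalance.

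This matters most for the secondary outcomes. The SAP expects about 148 end-point forms and 35 to 70 six-month forms, and accepts that power will be limited. About 257 baseline questionnaires are expected, and no planned model uses them. For the primary outcome the issue is one of rank: the more precise estimate is already planned, but it is not the one that carries the result.

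**Working it through.** **Inputs.** Significance level and power: "The above rest on the assumption that the alpha is equal to 0.05 and that the power is equal to 0.8". The test is two-sided ("to test the null hypothesis of equal means against the two-sided alternative"). Effect size: "The minimum detectable effect size is equal to 0.3", on the Cohen's d scale. Total 352, 1:1. Expected forms, from the SAP's Design overview: 257 at baseline (73%), 148 at end point, 35 to 70 at six months. The documents give no baseline-outcome correlation r, so r = 0.3, 0.5 and 0.7 are an assumed range.

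**1. The plan's own figure.** n per arm = 2 × (1.960 + 0.842)² / 0.3² = 2 × 7.849 / 0.09 = 174.4, so 175 per arm and 350 in total. The t-test version gives 175.4, so 176 per arm and 352 in total. Power at 176 per arm is 80.4%. The figure reproduces and takes no credit for covariates.

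**2. Effect of adjusting for baseline.** On the linear scale the residual variance is multiplied by 1 − r², that is 0.91, 0.75 or 0.51. Effective N is N / (1 − r²), and the detectable d at 80% power is 2.80 × √(4(1 − r²)/N).

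| r | 352 acts like | 148 acts like | Detectable d, 148 forms | Power for d = 0.3, 148 forms |
|---|---|---|---|---|
| 0 | 352 | 148 | 0.46 | 44.6% |
| 0.3 | 387 | 163 | 0.44 | 48.1% |
| 0.5 | 469 | 197 | 0.40 | 55.8% |
| 0.7 | 690 | 290 | 0.33 | 72.4% |

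The 148-form columns assume that every completer has a baseline form and that the six covariates already in equation (2) explain nothing. They are therefore upper limits on the gain.

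**3. Missing baseline forms.** Suppose that end-point completers have baseline forms at the overall 73% rate (an assumption).
- All 148 kept, by mean imputation with a missing indicator: the variance factor is 0.73(1 − r²) + 0.27 = 1 − 0.73r², which is 0.934, 0.818 or 0.642. Detectable d is 0.461 × √factor = 0.445, 0.416 or 0.369.
- Complete cases only: 0.73 × 148 ≈ 108 forms. This beats the unadjusted 148 only if (1 − r²)/108 < 1/148, so r² > 0.27 and r > about 0.52.

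**4. Six months.** Power for d = 0.3 with 70 forms goes from 24.0% to 26.0%, 30.5% or 42.0% across the three values of r. With 35 forms it goes from 14.2% to 15.2%, 17.5% or 23.7%.

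**5. Primary outcome as a count.** A simulation used 352 participants, the SAP's pilot control mean of 1.8, a rate ratio of 1/1.22, an assumed baseline mean of 3 and assumed lognormal heterogeneity. It fitted Poisson models with robust standard errors, with and without the log baseline count, in 600 runs per setting. The simulated baseline-outcome correlation ran from about 0.18 to 0.55. The standard error of the log rate ratio fell from 0.101 to 0.099 (2%) in the weakest setting and from 0.158 to 0.131 (17%) in the strongest.

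**The case against.** The strongest reply concerns the primary outcome. The unadjusted ITT estimate is unbiased under randomisation and is the analysis for which 352 was calculated. The baseline count is in a pre-specified regression and in the balance tests, so it will be reported. All of that stands. A reader might infer that the baseline police data are discarded, or that the headline is invalid; the SAP supports neither reading. Nor do the documents flatly contradict each other on this point. The Protocol also plans simple differences in means, names no headline, and refers to past offences rather than the 12-month contact count.

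For the secondary outcomes, the SAP calls the analysis exploratory and concedes low power, and equation (2) already has six covariates, including prior police contact. This limits the consequence and means that the true gain is the increment over those six. It does not explain why the most relevant covariate is absent.

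Two further inferences go too far. The Poisson mean in the Primary outcome analysis is written without a logarithm, which might suggest an identity link. The same section defines the link as the natural logarithm, and Presentation of outcomes takes the exponential of the coefficient, so this is a slip of notation. The SAP also says: "It is not clear a priori which distribution will be the better approximation, and therefore we consider below both scenarios". That might suggest that the headline distribution is wholly open. In fact the section goes on to favour Poisson, with Negative Binomial under overdispersion. The missing trigger for the normal model is a separate matter, and the case for baseline adjustment is the same under each distribution.

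**Conclusion.** The point holds in full for the secondary outcomes: baseline scores are collected before randomisation and no planned model uses them. For the primary outcome it holds for the headline only, where the baseline count is ranked second rather than lost. The consequence is lost precision and uncorrected chance imbalance, not bias.

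The size cannot be read from the documents because every r is assumed. For the secondary end point, the reduction in detectable d lies between small (0.46 to about 0.45 at r = 0.3 with 73% baseline coverage) and substantial (0.46 to 0.33 at r = 0.7 with full coverage and uninformative existing covariates). Adjustment would not rescue these outcomes: even the most favourable case leaves power for d = 0.3 at 72.4%. For the primary outcome, an effective sample of about 387 to 469 on the linear scale, or a 2–17% smaller standard error in the simulated count model, is a reasonable working range. The 690 obtained at r = 0.7 should not be cited as an expected gain, because it lies beyond the correlations that the count simulation reached.

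**What to change.** 1. **Equation (2).** Add the baseline value of the same SDQ or SRDS score, at end point and at six months, using the form completed before randomisation.
2. **Missing baseline scores.** State a rule that keeps these participants: multiple imputation, which the Missing data section already allows for control variables, or mean imputation with a missing indicator. Do not use complete cases.
3. **Balance table.** Add the five baseline scores.
4. **Primary headline.** Name the pre-specified model that includes prior-year contacts as the headline, and report the unadjusted estimate beside it. The functional form of the baseline count and the choice of count distribution are for the evaluators to settle; this point does not depend on them.
5. **Reporting.** Where Cohen's d comes from an adjusted model, take its interval from the regression coefficient. The interval formula in Presentation of outcomes depends only on d and the group sizes, so it would not show the gain.
6. **Erratum.** Write log(λᵢ) on the left of the Poisson mean equation in Primary outcome analysis.

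The cost is SAP wording, a little more analysis work and the rule for missing baseline scores. No new data are needed, though not every participant is expected to have a baseline form. The changes should be made before outcome data are examined.

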The planned number of the trial participants is 352 CYP in its two years of implementation, 176 in the RM group and 176 in the RC group. The sample size is such that the trial is sufficiently powered to detect a Cohen's d of at least 0.3. At the same time, the sample size is in line with the recruitment capacity, funder guidelines and the previous literature, see e.g. O'Connor and Waddell (2015) for a review. The mean effect sizes found in that paper for youth violence interventions range between 0.19-0.4. The calculations are done in Matlab based on Rosner (2011).

Table 3: Sample size calculations

⁷ Community resolution, Youth caution, Youth conditional caution, plus CYP who have been in contact with the police for a violent offence, but no further action has been taken.

		PARAMETER
Minimum Detectable Effect Size (MDES)		0.3
Alpha		0.05
Power		0.8
One-sided or two-sided?		Two-sided
Number of participants	Intervention	176
	Control	176
	Total	352

The above calculations report the sample size for the whole study over a two-year period.

Outcome measures

Primary outcome

The primary outcome of interest is the number of contacts of the CYP with the police, as perpetrators, victims or missing person episodes⁸. This will be measured using police administrative data from Greater Manchester Police (COGNOS system). Data will be taken for a period 1 year prior to the recruitment date and 3 months following the end of the interventions for each CYP. Police contact data is a discrete variable starting at 0.

This is a broad definition and was chosen because the CYP being referred to the RM or RC interventions were expected to have only had limited contact with the police. As a result, relying only on subsequent arrests and proven offending risked minimising their further contact with the police.

Secondary outcomes

The secondary outcomes will be the CYP's emotional and behavioural difficulties (as measured by the Strengths and Difficulties Questionnaire, SDQ) and self-reported delinquency (as measured by the Self-Report Delinquency Scale, SRDS).⁹ CYP will complete these at the point of consent, at the end of the interventions and 6 months

⁸ In cases where a CYP was arrested and rearrested for the same offence, we would create a rule that as this relates to the same offence, this would count as one arrest.

⁹ Full questionnaires for both the SDQ and SRDS are provided at Appendix 2.

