	
measure(s) (instrument, scale, source)
	
The first three scores are measured with the Strengths and Difficulties Questionnaire (SDQ). The remaining two scores (4 & 5) are measured with the Self-Reported Delinquency Scale (SRDS).
 
The SDQ and SRDS are completed by CYP at the point of consent, end of the intervention and 6 months after the end of the intervention as a follow-up (for CYP who start the interventions in the first 18 months of the trial).
 
For the SDQ CYP are asked to recall over the past 6 months, a period defined in the measure. For the SRDS, CYP are asked to recall over the past 3 months, this was a period defined for this study, in consultation with Remedi.
 
Scales are 0-20 for the internalizing and externalizing scores and 0-40 for the total difficulties score. Variety of delinquency ranges from 0-19 and volume of delinquency ranges from 0-198 (this excludes the scoring for Question 16, which is different from the other questions).
 
In the pilot study 73% of CYP consented into the interventions completed the initial questionnaires, and between one third and one half completed the end point questionnaires. We would expect these rates to be similar for this efficacy study and so could expect to receive around 257 initial questionnaires and 148 end point questionnaires. Six-month follow up questionnaires were not completed as planned during the pilot study and so we cannot use these completion rates to estimate the expected number of completed questionnaires during the efficacy study. However, we would expect completion rates to be lower than those at the end of the interventions, due to the break in contact with the CYP. As such we estimate between 10-20% of CYP will complete these questionnaires, which would equate to between 35-70 questionnaires. The expected attrition rate will affect the power of the analysis for these secondary outcomes.

Baseline for primary outcome
	
variable
	
The primary outcome of interest is the number of contacts of the CYP with the police, as perpetrators, victims or missing episodes.

	
measure (instrument, scale, source)
	
Police contact data will be taken from Greater Manchester Police administrative records for events 1 year prior to the intervention. Police contact data is a discrete count variable starting at 0.

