### **Missing data**

The primary outcome analysis will be performed according to the ITT principle (described above). The primary outcome is measured by police administrative data and therefore outcome variables for CYP that have disengaged with the intervention will still be collected, reducing concerns of missing values for the primary outcome variable. For the control variables that might be missing, we will follow YEF guidelines and in a first step we will attempt to establish the mechanism behind missingness using a logistic regression model. Depending on the pattern of missing data, either multiple imputation or sensitivity analyses will be conducted.

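### SDQ/SRDS results rest on questionnaire completers, about 58% expected missing: open to selection bias, baseline score omitted, and not an effect in one defined group

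*SAP*

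**What the plan says.** The SAP's Design overview expects "around 257 initial questionnaires and 148 end point questionnaires". The protocol (Outcome measures, Secondary outcomes) puts pilot completion at 73% for the initial questionnaires and 42% for the closing ones. The planned sample is "176 in the RM group and 176 in the RC group".

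Under Secondary outcome analysis, the SAP will "test the null hypothesis of equal means against the two-sided alternative" and fit linear regression (2). The covariates are "sex, age, ethnicity, district, prior contact with the police, and referral source". Baseline SDQ and SRDS scores are collected, as the Design overview shows, but they are not in that list.

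The section then says "we will only have outcome measures for CYP who complete the survey at the end of the treatment" and concludes that the estimate is the effect among CYP who finish the treatment. It labels the analysis exploratory and names reduced power as a limitation. It does not mention selection.

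The Missing data section covers the primary outcome, which comes from police records, and then covariates: "For the control variables that might be missing, we will follow YEF guidelines". It has no step for missing SDQ or SRDS outcomes. Longitudinal follow-up analyses repeats the same method at six months, where 10–20% completion is expected.

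**The concern.** Randomisation makes the two arms comparable as allocated. It does not make those who return a closing questionnaire comparable, because returning it happens after allocation and may depend on the programme received. RM asks a CYP to stay for 12 weeks at 3–4 sessions a week; RC asks for four sessions within one to four weeks. The CYP who last through each may differ in severity. Completing the survey is also not the same event as completing the treatment, yet the SAP moves from one to the other.

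At stake is the answer to the protocol's second research question. A difference, or the lack of one, in SDQ or SRDS could reflect who stayed and not what RM did, while the SAP's wording would present it as a treatment effect.

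**Working it through.** **Inputs.** From the documents: 352 CYP, 176 per arm; completion 73% (initial) and 42% (closing), or one third to one half (SAP, Design overview); alpha 0.05 two-sided, power 0.8, d = 0.3 (SAP, Sample size calculations overview). Assumed, because the documents give none: completion by arm, how completion depends on severity, and the baseline–outcome correlation.

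**1. The plan's own figures reproduce.**
- 352 × 0.73 = 256.96, i.e. 257. 352 × 0.42 = 147.84, i.e. 148.
- Missing at closing: 1 − 148/352 = 58.0%. With one third to one half completing (117 to 176 CYP), 67% to 50% are missing.
- Sample size: 2 × (1.960 + 0.842)² / 0.3² gives 175 per arm by the normal approximation; the t-based value is 175.4, i.e. 176. Power at 176 per arm is 0.804.

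**2. Precision with 148 completers (74 per arm if evenly split).** The standard error is √(2/74) = 0.164 SD. The detectable difference is 2.802 × 0.164 = 0.46 SD, and power for d = 0.3 is 45% (37% to 51% for 117 to 176 completers). The SAP acknowledges this loss of power. What follows it does not acknowledge.

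**3. What the completer difference estimates.** Let C(1) and C(0) indicate whether a CYP would complete the closing survey under RM and under RC, and Y(1), Y(0) the matching outcomes. The difference between completers is

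E[Y(1) | C(1)=1] − E[Y(0) | C(0)=1]
= {E[Y(1) − Y(0) | C(1)=1]} + {E[Y(0) | C(1)=1] − E[Y(0) | C(0)=1]}.

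The first bracket is an effect among those who would complete under RM. The second is selection. It vanishes only if the two completer groups have the same mean outcome under RC. The documents give no ground for assuming this: RM is 12 × 3 = 36 to 12 × 4 = 48 sessions, and RC is four.

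**4. How large the selection term could be.** Simulation with no true effect and 42% completing in each arm. Completion is logistic, falling with severity at the stated slope per SD. Negative values favour RM.

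| Completion depends on | Slope RM / RC | Correlation | Completer difference (SD) | After baseline adjustment (SD) |
|---|---|---|---|---|
| baseline | 0.5 / 0.5 | 0.6 | 0 | 0 |
| baseline | 0.5 / 0 | 0.3 | −0.08 | about 0 |
| baseline | 0.5 / 0 | 0.6 | −0.16 | about 0 |
| baseline | 1 / 0 | 0.6 | −0.29 | about 0 |
| baseline | 1 / 0.3 | 0.6 | −0.19 | about 0 |
| baseline | 0 / 0.5 | 0.6 | +0.17 | about 0 |
| outcome | 0.5 / 0 | 0.6 | −0.27 | −0.18 |
| outcome | 1 / 0 | 0.6 | −0.48 | −0.32 |

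At correlation 0.5, slopes of 0.5 and 1 in RM only give −0.14 and −0.24 SD. With a standard error of 0.164, a nominal 5% test would then reject a true null about 14% and 31% of the time.

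The near-zero entries in the last column for the baseline rows follow from the set-up, because completion there depends on baseline alone. The outcome rows show what adjustment cannot remove.

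**5. What baseline adjustment costs.** Only about 257 of 352 CYP are expected to have a baseline score. A complete-case regression that includes it could lose some of the 148 completers unless a rule keeps them.

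**The case against.** The case for the plan has substance. The SAP calls this analysis exploratory, confines its claim to finishers and says attrition will cost power. The primary outcome comes from police records and is unaffected. The protocol's Compliance section requires attrition at final data collection to be monitored and threats to internal validity to be documented. Prior police contact is already in equation (2), so the planned regression removes some selection on past behaviour; the simulated figures are for the raw difference, which the SAP also plans to test. If outcomes are missing at random given the covariates, an adjusted completer analysis is already valid, and imputation adds mainly what later police contacts contribute.

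All of that stands, and it limits the weight of the point. It does not rescue the interpretation. An exploratory label lowers the status of a result without changing what it estimates, and the finishers are not one group. The Compliance section of the SAP does assume that compliance does not vary with assignment, on the ground that CYP do not know their arm when they consent. That assumption serves the LATE, and ignorance at consent cannot secure equal completion once programmes of such different length begin.

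Two stronger readings are tempting. A reader might infer that the comparison is biased, and in favour of RM. The documents do not show this: completion is reported only pooled, equal selection gives zero, and reversed selection favours RC. A reader might also infer that adding the baseline score would cure the problem. It would not if completion depends on the outcome itself.

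**Conclusion.** The secondary analysis is open to selection bias, and the SAP's description of it as an effect among those who finish is unsupported whatever the completion pattern turns out to be. About 58% of closing outcomes are expected missing (50–67% on the SAP's looser wording).

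Size and direction cannot be computed from the documents. With completion slopes of 0.5 to 1 per SD of baseline severity in one arm only and a baseline–outcome correlation of 0.3 to 0.6, the bias under no true effect is about 0.08 to 0.29 SD. It favours whichever arm loses more of its severe cases, and it is zero if selection is equal. The upper end is close to the 0.3 SD the trial was sized to detect. Baseline adjustment removes the part explained by baseline; if completion depends on the outcome, about 0.18 to 0.32 SD remains at correlation 0.6. The slopes and correlations are assumptions throughout.

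The omitted baseline score is a plain gap, since the variable is already collected. The point concerns the secondary outcomes only, at closing and again at six months, where 35–70 questionnaires are expected.

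**What to change.** 1. Add the baseline score of the same scale to equation (2). State a rule that keeps completers whose baseline is missing, for example imputing the baseline or using a missing indicator, since only about 73% are expected to have one.
2. Replace the sentence claiming an effect among finishers with a statement that this is a comparison among questionnaire completers, not protected by randomisation. Report completion rates and the baseline characteristics of completers by arm.
3. As a sensitivity analysis, multiply impute the missing outcomes separately by arm, using baseline scores, police contacts before and after the intervention, and the covariates already listed. Add a delta shift to show how far the result depends on the missing-at-random assumption.

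No new data and no change to delivery are needed. The cost is SAP wording and some additional analysis. With about 74 observed outcomes per arm (148/2, if evenly split) and some baselines also missing, the imputed intervals will be wide and will rest on assumptions. That is why imputation is proposed as a sensitivity analysis and not as the main result.
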